4. PARTICIPANT ENTRY

Participants: entry criteria and sample size

All adults South Asian men and women living within the geographic boundaries of the selected surveillance site (as described by the relevant national administrative systems), will be invited to take part in the research. Recruitment targets (participants with appropriate consent, data and samples collected) by region to 2021 are provided in **Table 1**.

Inclusion criteria will be:

- 1. Age 18+ years
- 2. Male or Female
- 3. South Asian ancestry
- 4. Permanent resident of the surveillance site (resident for >12 months)

Exclusion criteria will be:

- Planning to leave the study site within the next 12 months
- Cancer or other serious illness expected to reduce life expectancy to less than 12 months

· Unable or unwilling to give consent

Table 1. Recruitment targets by country / region for the Surveillance study.

Region	Recruitment target	Partner organisations
Bangladesh	30,000	BRAC University, Dhaka
North India	30,000	DDF (Max Healthcare), Delhi
South India	40,000	Madras Diabetes Research Foundation, Chennai
Pakistan	30,000	Service Institute of Medical Science, Lahore Punjab Institute of Cardiology, Lahore King Edward Medical University, Lahore
Sri Lanka	30,000	University of Colombo, Colombo University of Kelaniya, Ragama

Recruitment

At each study site, governmental census data and other available household listings will be used, supported by house-house visits, to fully enumerate and identify the resident population. House-to-house visits will be done by the local primary care worker, in partnership with the research team. The purpose and potential benefits (personal and societal) of the surveillance will be explained. The research team will then obtain demographic details for the adult population of each household. People eligible and consenting to take part in the surveillance study will be asked to attend a nearby health facility in the fasting state, for the surveillance health assessment. Explanations of the project will be provided in writing and using videos, available in relevant South Asian languages, and supported by bilingual translators. We will also engage the community elders (eg teachers, employers, religious leaders) as trusted third parties, to support and facilitate engagement of the community in the study. Based on previous experience with population studies in these communities, participation rates are expected to exceed >70%; the availability of household enumeration data will enable participation to be monitored in detail, including by age, gender and major socio-economic groups.

Study procedures

Participants will be asked to attend in the morning after an overnight fast (water only after midnight). All participants will complete a structured assessment by trained members the dedicated research team, in five complementary domains: i. Registration and consent; ii. Questionnaire; iii. Physical measurements; iv. Biological samples and v. Clinical reporting. All study procedures implemented represent well established tools, that are validated for assessment of NCDs in population studies. The procedures will be carried out by trained research staff, using equipment and protocols that are standardized between countries and surveillance sites.

- i) Registration and consent. Written, informed consent will be obtained from all participants for data collection, and inclusion in the research. Informed consent will include permission for the data and samples collected to be used for NCD research, including data sharing with national and international bodies concerned with prevention and control of T2D and CVD, as well as for molecular epidemiological research. Consent will be facilitated using videos (available in major South Asian languages) and supported by bilingual translators. A unique study ID will be allocated to each participant.
- ii) **Questionnaire**. An interviewer administered health and lifestyle questionnaire will be used to collect information on behavioral risk factors (smoking, alcohol habit, physical activity and fruits/vegetables consumption), personal and family medical history, medications, socioeconomic status and knowledge of NCDs. The questionnaire is founded on the extended WHO

STEPS questionnaire that is widely used in global NCD surveillance,¹⁷ but adapted for use in South Asia, including through incorporation of additional questions. The interviewer administered questionnaires will be translated into locally relevant languages, and supported by graphics representations to facilitate collection of high quality data.

- iii) **Physical measurements**. Including: a) Anthropometry (height, weight, waist and hip circumference, and bio-impedance for body fat composition); b) Blood pressure by digital device; c) Cardiac evaluation by 12 lead ECG to identify arrhythmia, LVH and previous myocardial infarction; d) Retinal photography for assessment of retinal disease, including hypertensive and diabetic retinopathy; and e). Respiratory evaluation by spirometry to assess for smoking/environment-related lung injury.
- iv) **Biological samples**. We will collect venous blood samples (~20mls, by venesection using trained phlebotomists) for measurement of fasting glucose, lipid profile and HbA1c and other clinical relevant markers of cardiovascular health. This will comprise collection of blood into EDTA (~8ml), serum (~8ml) and citrate (~4ml) vacutainer tubes. An Oral Glucose Tolerance Test will be carried out in a subset of participants, enabling validation of diabetes classification by HbA1c. A spot urine sample (10ml) will also be collected for analysis of albuminuria and other biomarkers. Laboratory assays will be carried out using validated near-patient assays, and aliquots stored (-80C) for both external QC and future molecular epidemiological research.
- v) **Clinical reporting**. All results will be reviewed for clinically significant findings by a medically qualified member of the research team, who will also be responsible for ensuring that participants identified to have significant health conditions (e.g. T2D, hypertension) are referred to an appropriate facility for counselling and treatment. All study participants will receive a clinical report detailing the results of their health assessment, and the opportunity to discuss their results with the medical practitioner if significant abnormalities are present. To facilitate this, the clinical report will be made available to local community healthcare teams. Results will be accompanied by a booklet of explanation, and access to an explanatory video.

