This study will adhere to the principles outlined in the UK Policy Frame Work for Health and Social Care Research It will be conducted in compliance with the protocol, the Data Protection Act and other regulatory requirements as appropriate.

Table of Contents

1. INTRODUCTION	7
1.1 BACKGROUND	7
2. STUDY OBJECTIVES	9
3. STUDY DESIGN	9
4. PARTICIPANT ENTRY	11
5. ADVERSE EVENTS	13
5.1 DEFINITIONS	13
5.3 REPORTING PROCEDURES	13
6. STUDY TEM AND VISIT ORGANISATION	14
7. STATISTICS AND DATA ANALYSIS	17
8. REGULATORY ISSUES	19
8.1 ETHICS APPROVAL	19
8.2 CONSENT	19
8.3 CONFIDENTIALITY	19
8.4 INDEMNITY	19
8.5 SPONSOR	19
8.6 FUNDING	20
8.7 AUDITS	20
9. STUDY MANAGEMENT	20
10. DATA MANAGEMENT	20
PUBLICATION POLICY	22
10. REFERENCES	23
APPENDICES	24

GLOSSARY OF ABBREVIATIONS

ASHA	Accredited Social Health Activist
CC	Community Clinics
CEBs	Census enumeration blocks
CHT	Chittagong Hill Tracts
COPD	Chronic Obstructive Pulmonary Disease
CVD	Cardiovascular Disease
ECG	Electrocardiogram
EDTA	Ethylenediaminetetraacetic acid
GN	Grama Niladhari
ICT	Islamabad Capital Territory
NCD	Non-Communicable Disease
NIHR	National Institute for Health Research
LVH	Left Ventricular Hypertrophy
UD	Urban Dispensary
PMCU	Primary Medical Care Units
QC	Quality Control
SDMC	South Delhi Municipal Corporation
T2D	Type-2 Diabetes
WHO	World Health Organization

KEYWORDS

Cardiovascular Disease; Type-2 Diabetes; Surveillance

STUDY SUMMARY

TITLE Understanding the patterns and determinants of health in South Asian people - South Asia Biobank

DESIGN Cross-sectional study

AIMS We aim to establish a network of community based, NCD surveillance sites in Bangladesh, India North, India South, Pakistan and Sri Lanka

OUTCOME MEASURES Hypertension; diabetes; chronic kidney disease, CVD; stroke

POPULATION South Asian Population

ELIGIBILITY Inclusion criteria will be:

- Age 18+ years
- Male or Female
- South Asian ancestry
- Permanent resident of the surveillance site (resident for >12 months)

Exclusion criteria will be:

- Planning to leave the study site within the next 12 months
- Cancer or other serious illness expected to reduce life expectancy to less than 12 months
- Unable or unwilling to give consent

DURATION 20 years

REFERENCE DIAGRAM

[if appropriate]

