6. STUDY TEM AND VISIT ORGANISATION

We anticipate operating at least 2 surveillance teams per country / region (ie at least 10 teams total); the surveillance teams will rotate through the selected surveillance sites over the course of study. An expedited approach with greater initial effort may be used if appropriate, to achieve the same objective.

The typical composition (human resource) of the surveillance team is summarized in **Table 2**. The study equipment that will be used in summarized in **Table 3**.

Each surveillance team will work in a station based approach to maximise efficiency (**Figure 1**). The estimated duration of each station is shown; the surveillance health assessment is anticipated to take ~90 mins per person. We anticipate that each surveillance team will assess 25-40 participants per day; we thus anticipate screening 250-300 people per day across all sites (ie ~60,000 people per year, ~160,000 by Q1 2021).

[figure not shown]
Table 2. Typical composition of each surveillance team. Additional staff will be available for transportation and security, as required in respective local contexts.

Type of staff	Number	Job responsibility			
		Overall responsibility for the team			
Medical officer	1	Report on the clinical and laboratory data collected			
		Clinical guidance and counselling of participants			
Co-ordinator	1	Co-ordinate the team and oversee data collection			
Co-ordinator	ı	Implement quality control protocols			
		Registration and consent (1 Pax)			
		 Administer participant questionnaires (2 tables → 2 Pax) 			
Research Assistants /	5	 Anthropometry and blood pressure (1 Pax) 			
nurses		Assist Medical officer in clinical review (1 Pax)			
		Carry out household listing (afternoon activity, all)			
Phlebotomist	1	Collection of blood samples and urine samples			
		12 lead ECG (1 Pax)			
		Retinal photography (1 Pax)			
Laboratory technicians	4	Spirometry (1 Pax)			
		Analyse blood samples (1 Pax)			
		Process biological samples for storage (afternoon, all)			

 Table 3. Provisional equipment list for the surveillance project.

Measurement	Device	Number		
1. Core equipment (NCD "toolkit"; one toolkit per site)				
Height	Seca Wall Mounted Tape Measure	1		
Weight	Salter Electronic Scale	1		
Tape measure	Plastic tape measure	1		
Blood pressure	Omron device or Aneroid sphygmomanometer + stethoscope	1		
Glucometer	To be selected as a device in routine local use	1		
Tablet	7" Fusion5 Android Tablet or equivalent	1		

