7. STATISTICS AND DATA ANALYSIS

The key study indicators are based on the WHO NCD Global Monitoring Framework (Appendix 1). Therefore, we will follow the operational definition of the indicators, method of estimation, and guidelines for data disaggregation (by sex/socio-demographic stratifiers) proposed in the framework. As we will use a multistage sampling approach, appropriate sample weight will be estimated and used during the descriptive analysis.

Data will be analysed using appropriate statistical software (eg STATA, SPSS). Continuous variables will be assessed for normality, and non-normally distributed variables will be transformed as appropriate or will be assessed using non-parametric tests if appropriate. The data and samples collected will enable both cross-sectional and longitudinal analyses, and thus to define the prevalence and incidence of clinical outcomes of interest respectively. We will quantify the relationship between the clinical outcomes of interest, and potential underlying exposures (lifestyle, environmental, genetic) risk factors using regression techniques. For the assessment of relationship between a continuous primary and secondary outcome we will carry out mixed models analysis of covariance (e.g., BP, HbA1c, blood cholesterol, serum creatinine) etc. Mixed models logistic regression will be used to assess the association between explanatory and categorical outcome variables (e.g., T2D, CVD, hypertension, hypercholesterolemia). Regional differences within and between countries will also be explored. Statistical significance will be inferred at P<0.05, using techniques (eg Bonferroni) to control for multiple comparisons where appropriate. Power estimates for analyses of cross-sectional and longitudinal outcomes data are summarized in **Tables 4 and 5**.

Table 4. Power calculations for cross-sectional analyses. Results are expressed as i. the precision with which the prevalence for a clinical outcome of interest can be quantified and ii. the odds ratios (OR) detectable for association between a clinical outcome and an underlying exposure (exposure prevalence 20%, power 90%, P<0.05). Precision and power estimates are provide overall (N~160,000 people), at the level of the country (M~30,000 people), or at the level of the site (N~750 people). The table also summarized precision and power for low (~1%), intermediate (5-10%) and high frequency (~20-30%) outcomes of interest.

			Precision	OR detectable		

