Appendix 1. WHO Primary and secondary indicators for NCD prevention and control

The relevant core NCD surveillance indicators from the WHO Global Monitoring Framework, that will be directly captured in our surveillance study are as follows:

Domain	Indicators
Mortality and morbidity	 Unconditional probability of dying between ages of 30 and 70 from cardiovascular diseases, cancer, diabetes or chronic respiratory diseases
Behavioral risk factors	 Total (recorded and unrecorded) alcohol per capita consumption within a calendar year in litres of pure alcohol, as appropriate, within the national context Age-standardized prevalence of insufficient physically active persons aged 18+ years (defined as less than 150 minutes of moderate-intensity activity per week, or equivalent) Age-standardized prevalence of current tobacco use among persons aged 18+ years
Biological risk factors	 Age-standardized prevalence of raised blood pressure among persons aged 18+ years (defined as systolic blood pressure ≥140 mmHg and/or diastolic blood pressure ≥90 mmHg) and mean systolic blood pressure Age-standardized prevalence of raised blood glucose/diabetes among persons aged 18+ years (defined as fasting plasma glucose concentration ≥ 7.0 mmol/l (126 mg/dl) or on medication for raised blood glucose) Age-standardized prevalence of overweight and obesity in persons aged 18+ years (defined as body mass index ≥23 kg/m² for overweight and body mass index ≥ 28 kg/m² for obesity)
Behavioural risk factors	Age-standardized prevalence of persons (aged 18+ years) consuming less than five total servings (400 grams) of fruit and vegetables per day
Biological risk factors	 Age-standardized prevalence of raised total cholesterol among persons aged 18+ years (defined as total cholesterol ≥5.0 mmol/l or 190 mg/dl); and mean total cholesterol concentration
Drug and counseling	 Proportion of eligible persons (defined as aged 40 years and older with a 10-year cardiovascular risk ≥30%, including those with existing cardiovascular disease) receiving drug therapy and counselling (including glycaemic control) to prevent heart attacks and strokes Proportion of people with hypertension receiving drug therapy and counselling Proportion of people with diabetes receiving drug therapy and counselling

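### The only glucose device listed is a glucometer of local choice, despite the promise of standardised equipment, and the OGTT subset is tied to an HbA1c classification that the adopted diabetes indicator does not use

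*Protocol*

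**What the plan says.** Diabetes is one of the outcome measures in the Study Summary: "Hypertension; diabetes; chronic kidney disease, CVD; stroke". Table 4 gives it an expected prevalence of 20%.

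**Definition.** Section 7 says of the key WHO indicators that "we will follow the operational definition of the indicators, method of estimation". Appendix 1 gives the diabetes indicator as "defined as fasting plasma glucose concentration ≥ 7.0 mmol/l (126 mg/dl) or on medication for raised blood glucose". HbA1c is not part of it. Section 4 (Biological samples) takes venous blood "for measurement of fasting glucose, lipid profile and HbA1c" and adds an OGTT in a subset, "enabling validation of diabetes classification by HbA1c". It states no HbA1c cut-off. Section 7 also lists T2D as a categorical outcome for mixed logistic models, without a definition.

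**Device.** Section 4 (Study procedures) says the work will be done "using equipment and protocols that are standardized between countries and surveillance sites". Table 3 in section 6, headed as provisional, has two parts. The core toolkit, one per site, contains the glucometer: "To be selected as a device in routine local use". The special equipment, one set per surveillance team, names an HbA1c analyser and a lipid analyser and has no row for glucose.

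**The concern.** The Appendix 1 rule is a fixed cut on a continuous measurement. Where many people lie near the cut, a small proportional error in the instrument moves many of them across it. If the instrument is chosen locally, that error can differ by region, and it is then confounded with region. Section 7 plans to explore differences within and between countries. The Appendix 1 indicator on treatment of people with diabetes uses the same case definition as its denominator, so both results would carry the device effect. A larger sample does not reduce it.

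The second issue is smaller. The only diabetes validation exercise in the protocol is described in terms of HbA1c. Both markers are measured, so some participants will be positive on one and negative on the other. Nothing says what role HbA1c then has, or which definition T2D takes in the regression models.

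**Working it through.** **1. The plan's own figure.** Table 4, diabetes row: precision 0.2% overall, 0.5% by country, 2.9% by site. Formula: 1.96 × √(p(1−p)/N) with p = 0.20.

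- N = 160,000: 1.96 × √(0.16/160,000) = 0.196%
- N = 30,000: 1.96 × √(0.16/30,000) = 0.453%
- N = 750: 1.96 × √(0.16/750) = 2.863%

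All three reproduce. They cover sampling error under simple random sampling and contain nothing for measurement bias. On the same basis, a difference between two regions of 30,000 has half-width 1.96 × √(2 × 0.16/30,000) = 0.64 points.

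**2. What Table 3 lists for each measure.**

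| Measure | Per-site toolkit | Per-team set |
|---|---|---|
| Weight | yes | yes, named |
| Blood pressure | yes | yes, named or equivalent |
| HbA1c | no | yes, named |
| Lipids | no | yes, named |
| Height | yes, named | no |
| Glucose | yes, local choice | no |

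Weight and blood pressure have a second entry in the team set. Glucose does not. Height also has its only row in the toolkit and is a study measurement under section 4, so toolkit items plausibly serve as study instruments. The height row names a device; the glucose row leaves the choice to local practice.

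**3. Size of a device effect. The documents give no bias figure, so every input here is assumed.** Let fasting glucose in untreated adults be log-normal with log-SD s, and let a proportion P lie at or above 7.0 mmol/l. Put z = Φ⁻¹(1−P). A meter reading a factor (1+b) too high gives an apparent proportion 1 − Φ(z − ln(1+b)/s). With ln 1.05 = 0.0488 and ln 0.95 = −0.0513:

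| P | s | z | +5% bias | −5% bias |
|---|---|---|---|---|
| 8% | 0.18 | 1.405 | +4.8 | −3.5 |
| 8% | 0.22 | 1.405 | +3.8 | −2.9 |
| 12% | 0.18 | 1.175 | +6.3 | −4.8 |
| 12% | 0.22 | 1.175 | +5.0 | −4.1 |

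Worked case: P = 12%, s = 0.18, b = +5% gives 1 − Φ(1.175 − 0.271) = 1 − Φ(0.904) = 18.3%, up 6.3 points.

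These are percentage points among untreated adults. People on medication count as cases whatever the meter reads, so in the whole population the shift is multiplied by the untreated share. With 10% treated (assumed), 2.9 to 6.3 becomes 2.6 to 5.7. A 1% bias under the same inputs gives about 0.7 to 1.1 points either way among untreated adults, still above 0.5.

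**4. The definition.** Section 7 adopts the framework definitions, and Appendix 1 gives fasting glucose or medication, so the WHO prevalence and treatment indicators have one rule. Section 4 describes the OGTT as validating HbA1c classification. T2D in the models has no stated rule. No passage connects these three statements.

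**The case against.** **On the device.** No passage says that the 7.0 mmol/l threshold is read on the local glucometer. Section 4 describes venous blood and validated near-patient assays, and Table 3 is provisional. The toolkit is separate from the rotating team's set and even allows an aneroid blood pressure device, whereas section 4 specifies a digital one, so a toolkit item is not automatically the study instrument. This stands, and a reader who infers that study glucose is certainly measured on local meters goes beyond the text. What remains is that the protocol lists no other glucose device and names no common assay.

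**On safeguards.** The quality-control text in section 6 requires regular calibration and checks for drift or bias between machines and observers, and allows re-testing of samples. These reduce the risk, and the illustration assumes a bias that escapes them. They still do not set one assay across regions. The aliquots stored for external QC do not clearly fill the gap. Blood is taken in the morning and Table 2 puts processing for storage in the afternoon, and the documents do not show that such aliquots give a valid glucose reference.

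**On the definition.** A reader might infer two conflicting diabetes rules. The text does not support that: section 4 gives no HbA1c cut-off, and section 7 already settles the WHO indicators in favour of Appendix 1. Measuring both markers is compatible with that. The definition of T2D in the models could fairly be left to a statistical analysis plan. Taken alone, this part is close to missing detail; what stands is that the stated purpose of the OGTT does not match the adopted indicator.

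**Conclusion.** The point holds in two limited parts.

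The firmer part is the device. A locally chosen glucometer as the only listed glucose instrument contradicts the statement on standardised equipment, for the measurement on which the Appendix 1 diabetes threshold depends. If such meters are used and differ by 5% without correction, prevalence among untreated adults moves by about 3 to 6 points against a stated country precision of 0.5. That range rests wholly on assumed inputs: the 8-12% above threshold, the log-SD, and the bias itself. It shows scale and does not predict an error. No stated figure in Table 4 is wrong on this point.

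The lesser part is that the role of HbA1c and of the OGTT subset is not reconciled with the adopted indicator. No size should be attached to it: people positive only on glucose and people positive only on HbA1c offset each other, and the documents give no figure for either group.

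This is a cheap improvement worth making; the design does not fail without it.

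**What to change.** 1. In Table 3, move glucose to the per-team standard set and name one plasma-calibrated assay for all five regions. State in section 4 that this assay provides the fasting glucose used for classification.
2. In section 7, state that the Appendix 1 definition is primary for diabetes prevalence and for T2D in the regression models, and that classification by HbA1c is a secondary definition with its cut-off given.
3. In section 4, reword the purpose of the OGTT subset so that it is compared with both the fasting-glucose and the HbA1c classifications.

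Cost: one common device for about 10 teams (section 6 plans at least two per region), plus protocol wording. No extra visit, sample or staff is needed. The downside of item 1 is giving up the convenience of a device already in routine local use.
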